5. STATISTICAL ANALYSES

5.1. General Considerations

A baseline (or reference) value will be defined as the value of the last available assessment prior to the first vaccination on Day 1, where Day 1 is the date of first vaccination for adults. A value at birth is baseline value for neonates and the birth date is the neonate reference date. The neonate baseline values for immunogenicity analysis are those from the cord blood sample collected.

Every adult will have a unique subject ID in the ADaM datasets and every neonate will have the same unique subject ID with 'A' added at the end of the ID. Multiple pregnancies [twins or higher order multiples] are excluded from the study but if a participant with multiple pregnancy is inadvertently enrolled, neonates will have the same unique subject ID with 'A', 'B', 'C' and D added at the end of the ID based on the number of neonates.

Unless otherwise specified, continuous variables will be summarized using the following statistics, as appropriate: number of observations, arithmetic mean (mean), standard deviation (SD), standard error (SE), median, minimum, and maximum. Frequencies and percentages (one decimal place) will be generated for categorical variables. Denominator for the percentages is the number of participants in the considered population, and phase (where applicable; incidence per 100 participants/phase).

No formal statistical testing is planned. The safety analysis will be performed on the FAS-A based on actual intervention received and the FAS-NVN, unless otherwise specified. Safety data will be presented by period/phase (as applicable) as well as over the entire study. Immunogenicity results will be conducted on the PPI-A and PPI-NVN and presented per scheduled time point as appropriate. Safety and immunogenicity endpoints will be summarized descriptively by previous vaccination group (as defined in Section 1.2) and overall. All listings will include the previous vaccination group. Vaccination schedule in Group 4 (i.e. vaccine-naive at study entry) will have two components: the Primary Vaccination and the (optional) Booster Vaccination. Listings will be shown per phase and time point, as appropriate.

Participants that took another COVID-19 vaccine during the study are excluded from all safety and immunogenicity analyses from the moment they received the other vaccine. The safety data from those participants after they received the other vaccine will be listed separately.

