follow-up 2'

max PN D183

(neonates); i.e. PN D43 to

	Phase		Period		Interval
Phase	#	Period	#	From	То
'Postnatal follow-up 3' (neonates); i.e. PN D183 to max PN D366	7			One minute after Postnatal follow-up 2 period ends	 Minimum of : g) Maximum of 23:59 at the date of last contact (for early discontinuation) and 23:59 at the date of last visit h) 23:59 at the date of data base cut-off date in case of interim analysis i) D366 after birth j) One minute before date and time of another COVID-19 vaccination outside the study k) One minute prior to end of the study visit
'Post-dose' (Booster)	2	Post-dose 2 (i.e. Post- Booster)	2	Date and time of second vaccination (i.e. Booster)	 Minimum of: a) 23:59 at the date of last contact (for early discontinuation) b) 23:59 at the date of data base cut-off date in case of interim c) 23:59 on 28 days after the Booster Vaccination (23:59 of that day + 28 days) d) One minute before date and time of another COVID-19 vaccination outside the study
Booster follow-up 1	8			One minute after post-dose 2 period ends	 Minimum of: a) 23:59 at the date of last contact (for early discontinuation) b) 23:59 at the date of data base cut-off date in case of interim c) One minute prior to 6 months after Booster Vaccination d) One minute before date and time of another COVID-19 vaccination outside the study
Booster follow-up 2	9			One minute after Booster follow-up 1	 Minimum of: a) Maximum of 23:59 at the date of last contact (for early discontinuation) and 23:59 at the date of last visit b) 23:59 at the date of data base cut-off date in case of interim c) One minute before date and time of another COVID-19 vaccination outside the study e) One minute prior to end of the study visit
Follow-up other vaccine	10			Date and time of viral vaccination outside the study	 Minimum of: a) Maximum of 23:59 at the date of last contact (for early discontinuation) and 23:59 at the date of last visit b) 23:59 at the date of data base cut-off date in case of interim analysis c) Date and time of end of the study visit

Note: PP Dx = Postpartum Day x, PN Dx = Postnatal Day x

Adverse Events (AE) tables and selected other tables may display AEs (or other counts) by phase. For such tables, post vaccination periods can be combined and additionally displayed. The "active" periods can be defined as:

- "Post-Dose 1"
- "Post-Booster", where applicable (booster)
- "Post-Dose 1 and Post-Booster Combined", where applicable.

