5.6.1.4. Phase Allocation of Adverse Events

Solicited events are always allocated to the respective Post-dose period.

Step 1: Allocation of events to the periods:

Adverse events in the SDTM database are allocated to periods based on their start date/time. If the start date/time of an event falls between (or on) the start and stop date/time of a period, the AE is attributed to that period (treatment-emergent principle).

- In case of partial start or stop dates (i.e. time and/or day and/or month and/or year missing), the events are allocated to the periods using the available partial information on start and end date; no imputation will be done. If, for instance, the AE start date only month and year are available, these data are compared to the month and year information of the periods. This rule may lead to multiplication of the event as a consequence of its assignment to multiple periods.

- In case of a completely missing end date, the date is imputed by the cut-off date of the analysis for participants still ongoing in the study, and by the end date of the last period for participants who discontinued or completed the trial. In case of a completely missing start date, the event is allocated to the first active treatment phase (post-dose 1 period), except if the end date of the AE falls before the start of the first active treatment phase (post-dose 1 period).

Step 2: Combination of events:

Overlapping/consecutive events are defined as events of the same participant with the same preferred term which have at least 1 day overlap or for which the start date of an event is 1 day after the end date of the preceding event. Overlapping/consecutive events may be combined into one AE or not, according to the following rules:

1) If overlapping/consecutive events start in one of the following periods - Screening or post-dose extension (i.e. non-active periods) - followed by an AE in - post-dose period (active period) - they are allocated to their respective periods and are considered as separate events.

2) In case overlapping/consecutive events start within a single period, they are considered as one and the same AE. The individual events which contribute to this AE are retained as individual

records in the ADaM database but are assigned the same onset, period, and total duration. All related attributes to the AE/phase/period should also be consistent with the new event.

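### Table 3 opens the Follow-up other vaccine phase at any viral vaccination, but closes the other post-vaccination phases only for another COVID-19 vaccination, so phases can overlap

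*SAP*

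**What the plan says.** Table 3 in SAP Section 5.1.2 gives the start of Phase 10, Follow-up other vaccine, as "Date and time of viral vaccination outside the study". Viral vaccination is not defined, and the term is used nowhere else in the SAP.

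The other post-vaccination rows use a narrower trigger for outside vaccines: "One minute before date and time of another COVID-19 vaccination outside the study". This applies to Post-dose 1, Prepartum follow-up 1, Postpartum/Postnatal follow-up 1, Postpartum/Postnatal follow-up 2 (where the table text is displaced in the copy read), Postnatal follow-up 3, Post-dose 2, and Booster follow-up 1 and 2. Screening has no such rule and needs none, since it ends before the first dose.

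Section 5.1 uses the same narrower trigger: "Participants that took another COVID-19 vaccine during the study are excluded from all safety and immunogenicity analyses from the moment they received the other vaccine". It adds: "The safety data from those participants after they received the other vaccine will be listed separately". The per-protocol rule in Section 5.1.3 and the disposition list in Section 5.2 likewise name only another COVID-19 vaccine.

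Section 5.6.1.4 allocates adverse events by start date: "If the start date/time of an event falls between (or on) the start and stop date/time of a period, the AE is attributed to that" interval.

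**The concern.** A phase structure for by-phase safety tables should place each fully dated event in one phase. Here the event that opens Phase 10 is wider than the event that closes the phases before it. A participant who receives a viral vaccine other than a COVID-19 vaccine (an influenza vaccine, for instance, although the SAP names none) would start Phase 10 while her current phase continues and later phases open as usual.

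Two by-phase outputs would be affected. Her later unsolicited events would appear both in the phase where they belong and in Phase 10. She would also be counted in Phase 10, both in the number of participants per phase (Section 5.2) and in the Phase 10 denominator, since Section 5.1 bases percentages on the participants in the population and phase. Phase 10 would then mix two kinds of participant: those censored under Section 5.1, and those who properly remain in the main analysis.

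**Working it through.** The plan states no figure on this point, so the check is to apply its rules to one case.

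**Rules used.** The adult rows of Table 3, and the rule in Section 5.6.1.4 that an event belongs to a period when period start ≤ event start ≤ period stop.

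**Assumed dates (illustrative, not from the SAP).** First dose 10 Jan 2022, birth 20 Apr 2022, end-of-study visit 21 Apr 2023, outside vaccine 25 Jan 2022. No booster. Five unsolicited events, on 15 Jan, 30 Jan, 1 Mar, 1 May and 1 Sep 2022.

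**Phase limits when the outside vaccine is not a COVID-19 vaccine.**
- Post-dose 1: 10 Jan to 10 Jan + 28 days = 7 Feb 2022, 23:59.
- Prepartum follow-up 1: from one minute later to one minute before birth on 20 Apr 2022. Birth comes before the six-month limit in July.
- Postpartum follow-up 1: 20 Apr to 20 Apr + 42 days = 1 Jun 2022.
- Postpartum follow-up 2: from one minute later to postpartum Day 366 = 20 Apr 2023.
- Phase 10 as written: 25 Jan 2022 to the end-of-study visit on 21 Apr 2023.

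**Allocation.**

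| Event start | Non-COVID viral vaccine, Table 3 as written | Same vaccine, COVID-19-only trigger | Outside COVID-19 vaccine on the same date |
|---|---|---|---|
| 15 Jan 2022 | Post-dose 1 | Post-dose 1 | Post-dose 1 |
| 30 Jan 2022 | Post-dose 1 and Phase 10 | Post-dose 1 | Phase 10 |
| 1 Mar 2022 | Prepartum follow-up 1 and Phase 10 | Prepartum follow-up 1 | Phase 10 |
| 1 May 2022 | Postpartum follow-up 1 and Phase 10 | Postpartum follow-up 1 | Phase 10 |
| 1 Sep 2022 | Postpartum follow-up 2 and Phase 10 | Postpartum follow-up 2 | Phase 10 |

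As written, 4 of the 4 events after the outside vaccine fall in two phases. With the narrower trigger, 0 of 5 do. With an outside COVID-19 vaccine the earlier phase closes one minute before Phase 10 opens and no event is allocated twice, which indicates how the table was meant to work.

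**Is there a rule that resolves the overlap?** Section 5.6.1.4 gives no priority between overlapping periods. It foresees multiple assignment only for partial dates, where it warns: "This rule may lead to multiplication of the event as a consequence of its assignment to multiple periods". The events above are fully dated.

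**Which outputs change?** The woman stays correctly in her main phases, so those rows keep their numerators and denominators. The Phase 10 row gains events and a participant it should not have. General unsolicited-event tables are limited to 28 days after vaccination (Section 5.6.1.3). Of the four doubled events, only the one on 30 Jan would therefore enter those tables. The later ones would be tabulated only if they were serious, of special interest, led to discontinuation, or were medically attended within the six-month window.

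**The case against.** The strongest reply is that the intended meaning can be recovered from the SAP itself. The phase is named Follow-up other vaccine. In Section 5.1 the other vaccine refers back to another COVID-19 vaccine, and the outside-vaccine stop rules, the per-protocol rule and the disposition list all agree. A careful programmer may well read the cell that way. This stands as far as intent goes, and it makes the point a drafting inconsistency. It does not remove the point, because Table 3 is the derivation rule and its literal application gives a different result.

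A reader might also infer wider damage than the document supports:

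- **That every later adverse event is doubled.** Section 5.6.1.4 always keeps solicited events in their Post-dose period, so only unsolicited events are exposed.
- **That the main safety results are inflated.** The active periods defined after Table 3 are Post-Dose 1, Post-Booster and the two combined. None of the four Table 4 intervals, Entire Study included, contains Phase 10. Whole-study participant counts are therefore not doubled.
- **That the separate listing is contaminated.** Section 5.1 defines that listing by its own COVID-19 trigger and does not refer to Phase 10. It would be affected only if someone programmed it from Phase 10 and disregarded Section 5.1.
- **That the share of Phase 10 wrongly filled can be estimated.** The SAP gives no uptake of either kind of vaccine, so any percentage would restate the assumed inputs. Head counts based on 240 would use a recruitment target, and Sections 1.2 and 3 state that enrolment ceased as of protocol amendment 7.

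**Conclusion.** The inconsistency is real and minor. Applied literally, Table 3 lets Phase 10 overlap the main phases after a non-COVID viral vaccine. Later unsolicited events are then allocated twice, and Phase 10 mixes uncensored with censored participants. A participant who received a non-COVID viral vaccine and later an outside COVID-19 vaccine would also have Phase 10 start too early. The row is not restricted to adults, so the same mismatch stands against the postnatal phases.

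The effect is confined to the Phase 10 row of by-phase tables and the per-phase head count. It depends on two things the SAP does not settle: that a non-COVID vaccine is counted as a viral vaccination, and that some participants receive one during follow-up. Its frequency cannot be derived from the document.

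**What to change.** In Table 3, make the start of Phase 10 the date and time of the same event that closes Phases 2 to 9, namely the COVID-19 vaccination named in "One minute before date and time of another COVID-19 vaccination outside the study", without the one-minute offset. Phase 10 then begins where the preceding phase ends and agrees with Section 5.1.

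The cost is one table cell and the matching line of the phase-derivation program, before database lock. No new data are needed and no endpoint or analysis set changes.

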5.1.2.1. Other time intervals

The following other time intervals will be derived for safety data summary as shown in Table 4.

Time Intervals	From	То
Up to Postpartum Day43	Date and time of first	Maximum of:
	vaccination	a) Post-dose 1 end date
		b) Prepartum follow-up 1 end date
		c) Postpartum follow-up 1 end date
Primary Vaccination Period	Date and time of first	Maximum of:
(in vaccine naïve group only)	vaccination	a) Post-dose 1 end date
		b) Prepartum follow-up 1 end date
		c) Postpartum follow-up 1 end date
		d) Postpartum follow-up 2 end date
Booster Vaccination Period	Date and time of Booster	Maximum of:
(in vaccine naïve group only)	Vaccination	a) Post-dose 2 end date
		b) Post Booster follow-up 1 end date
		c) Post Booster follow-up 2 end date
Entire Study	Date and time of first	Maximum of:
	vaccination	a) Primary Vaccination Period end date
		b) Booster Vaccination Period end date

Table 4:Other Time Intervals

5.1.3. Visit Windows

The following visit window rules must be taken into consideration when deriving the PPI-A and PPI-NVN. Note that if an immunogenicity sample is not taken, the corresponding protocol deviation will be considered to have no impact on immunogenicity.

For adult immunogenicity sampling (Note: PP=Postpartum):

- 1. If a participant is not vaccinated with the study vaccine, all immunogenicity samples taken will be excluded
- 2. If the scheduled booster vaccination was given ≤ 60 days from last study vaccination, all immunogenicity samples taken on and after the booster will be excluded from the PPI (Samples taken before may still be included in the PPI).
- 3. For the following visits, if an immunogenicity sample is taken out of below-defined windows, the sample will be excluded from PPI. Other samples from this participant may still be included in PPI.
 - Adult Study D29 sampling: sample excluded from PPI if outside of +/-10 days from planned blood collection date.
 - Adult 'Birth visit' (PP D1): sample excluded from PPI if outside of +7/-2 days from planned blood collection date.
 - Adult Follow up period PP D43, and PP D183 sampling: sample excluded from PPI if outside +/-30 days from planned blood collection date.
- 4. Adult Booster vaccination (Pre-Booster D1) sampling (if applicable): sample excluded from PPI if taken ≤ 60 days from study vaccination.
- 5. Adult Booster vaccination (Post-Booster D29) sampling: sample excluded from PPI if outside of +/-10 days from planned blood collection date.

For neonate/infant immunogenicity sampling (Note: PN=Postnatal)

- 1. For the following visits, if immunogenicity samples are taken out of below-defined windows, the samples will be excluded from PPI. Other samples from this participant may still be included in PPI.
 - Neonate/infant PN61 sampling: sample excluded from PPI if outside of +/-14 days from planned blood collection date.
 - Neonate/infant PN6mo and PN12mo sampling: sample excluded from PPI if outside +/-30 days from planned blood collection date.

If an adult participant had another COVID-19 licensed vaccine, or used a disallowed medication, all samples after such (major) protocol deviation with impact on immunogenicity will be excluded from the PPI-A. In the case such protocol deviation occurs for the adult participant before and up to child delivery, all samples from the neonate will be excluded from PPI-NVN. Depending on the type of other protocol deviation, all samples collected after the protocol deviation, or the sample relating to the time of protocol deviation only will be excluded from PPI. This will be further clarified in the DPS.

Time windows may be redefined prior to database lock if the number of samples excluded as per the definitions above are too numerous. No time windows apply for Early Exit visit sampling. The sample closest to the target day (at noon) will be selected, if two or more samples meet the PPI definition in the pre-defined time windows.

5.2. Participant Dispositions

The number and percentage of adult participants in the following disposition categories will be summarized throughout the study by vaccine regimen and overall:

- participants screened
- participants screen failed (and main reason for screen failure)
- participants vaccinated (Primary/Booster)
- participants not vaccinated
- participants in the FAS-A
- participants in the PPI-A
- participants in the FAS-A but not in the PPI-A (and reason for not being in the PPI-A)
- participants who discontinued the study (and reasons for discontinuation)
- participants having another COVID-19 vaccine during the study

The number of neonates/infants in the FAS-NVN and PPI-NVN will also be tabulated.

Also, the number of participants and percentage per phase will be tabulated.

5.3. Primary Endpoint(s) Analysis

5.3.1. Definition of Endpoints

Safety and reactogenicity of Ad26.COV2.S (first vaccination) in adult participants

- Solicited local and systemic AEs for 7 days after (first) vaccination, or until resolution
- Unsolicited AEs for 28 days after (first) vaccination
- SAEs and AESI throughout the study (from first vaccination until end of the study, i.e. at least 12 months after delivery)
- MAAEs until 6 months after the last vaccination
- AEs leading to study discontinuation (during the entire study)

Refer to Sections 5.6.1 for more details on adverse events definitions.

Humoral Immune Response in peripheral blood of adult participants

• Serological response to vaccination as measured by enzyme-linked immunosorbent assay (ELISA; [S-ELISA, EU/mL]), 28 days after vaccination

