1.1. Objectives and Endpoints

Objectives	Endpoints
Primary	
To assess the safety and reactogenicity of Ad26.COV2.S administered intramuscularly	• Solicited local and systemic AEs for 7 days after vaccination, or until resolution.
(IM) as a 1-dose (5×10 ¹⁰ vp) schedule in adult participants, during the 2 nd and/or 3 rd trimester of pregnancy, and (potentially) postpartum.	• Unsolicited AEs for 28 days after vaccination.
	• Serious adverse events (SAEs) and Adverse Events of Special Interest (AESI) throughout the study (from vaccination until end of the study, i.e., at least 12 months after delivery).
	• Medically-attended adverse events (MAAEs) until 6 months after vaccination
	• AEs leading to study discontinuation (during the entire study).
To assess the humoral immune response in peripheral blood of adult participants to Ad26.COV2.S administered IM as a 1-dose $(5 \times 10^{10} \text{ vp})$ schedule, during the 2 nd and/or 3 rd trimester of pregnancy, 28 days after vaccination.	• Serological response to vaccination as measured by enzyme-linked immunosorbent assay (ELISA; [S-ELISA, EU/mL]), 28 days after vaccination.
Secondary	
Adults	
To assess safety of the booster dose of Ad26.COV2.S at 5×10^{10} vp on participants	• Solicited local and systemic AEs for 7 days after booster vaccination, or until resolution.
who were vaccine naïve at study entry.	• Unsolicited AEs for 28 days after vaccination.
	• SAEs and AESI throughout the study (from vaccination until end of the study, i.e., at least 12 months after delivery).

Objectives	Endpoints
	MAAEs until 6 months after vaccination
	• AEs leading to study discontinuation (during the entire study).
To assess pregnancy outcomes in adult participants who have received Ad26.COV2.S during the 2 nd and/or 3 rd trimester of pregnancy.	• Pregnancy outcomes (including, live term birth, live preterm birth, stillbirth, and abortion) (non-exhaustive).
To assess pregnancy-related AEs in adult participants who have received Ad26.COV2.S during the 2 nd and/or 3 rd trimester of pregnancy.	• Pregnancy-related AEs throughout pregnancy (including gestational diabetes, gestational hypertension, premature rupture of membranes, premature labor, premature uterine contractions, poor or restricted fetal growth, pre-eclampsia, eclampsia, vaginal or intrauterine hemorrhage) (non-exhaustive).

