There will be no active vaccination with Ad26.COV2.S of neonates/infants in this study.

Previously vaccinated participants (Groups 1-3), will receive a single dose of Ad26.COV2.S at 5×10^{10} vp as part of the study. No further vaccinations will be received by these groups during the study.

A booster vaccination with a single dose of Ad26.COV2.S at 5×10^{10} vp will be offered to vaccine naïve consenting participants who have completed pregnancy, are not pregnant again, and haven't received another COVID-19 vaccine (eg, national immunization program). The booster vaccination for vaccine naïve participants at study entry should be administered not earlier than 2 months after the participant's Ad26.COV2.S vaccination in the study. The study duration will not be extended. Dose 2, in this document refers to Booster which is only applicable for Group 4.

Safety assessments include an observation period at the study site after vaccination to monitor for the presence of any severe acute reactions, the recording of any solicited local or systemic adverse events (AEs), unsolicited AEs, serious AEs (SAEs), adverse events of special interest (AESI), pregnancy-related AEs throughout pregnancy, and medically attended adverse events (MAAEs).

Other safety assessments include clinical laboratory assessments, vital signs measurements (pulse/heart rate, supine systolic and diastolic blood pressure, respiratory rate, and body temperature) and physical examinations. In addition, adverse maternal/fetal outcomes, adverse neonate/infant outcomes SAEs (including MIS-C), MAAEs and AEs leading to discontinuation will be recorded.

Active surveillance for COVID-19-like signs and symptoms in participants and neonates/infants will occur, including a COVID-19 surveillance (symptom check) through the participant's electronic diary (electronic clinical outcome assessment [eCOA]). Participants will be asked to confirm whether subjective changes in (postpartum) breast milk production (reduction) have been noticed and report changes in the eCOA diaries. Confirmed SARS-CoV-2 infection will be recorded.

Individuals who do not meet the criteria for participation in this study (screen failure) may be rescreened on 1 occasion only. Participants who are rescreened will be assigned a new participant number, undergo the informed consent process, and then restart a new screening phase.

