5.3.3. Analysis Methods

Safety and reactogenicity of Ad26.COV2.S in adult participants

The primary safety and reactogenicity objectives for adult participants of the study will be evaluated with AEs, SAEs, AESIs and MAAEs as detailed in Section 5.6.1 for definitions and analyses methods of adverse events.

Refer to Section 5.7.1 for definitions and analyses methods of immunogenicity endpoints.

Analyses will also be performed by subgroup: gestational age group, participant age group at baseline, and the SARS-CoV-2 serostatus at baseline. Refer to Section 5.7.5 for subgroup definitions.

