5.6.1.3. Analysis of Adverse Events

Solicited AEs (shown in output) are extracted from the investigator assessment pages of the CRF and will be recorded in the Clinical Event SDTM domain. Only Solicited AEs with onset within 7 days after vaccination (post-dose 1, post-booster [booster in Group 4], and post-dose 1+ post-booster) will be reported in tables. For unsolicited AEs, only the AEs within the 28-day period following (primary or booster) vaccination will be presented in the safety tables except for SAEs, AEs leading to treatment/study discontinuation (incl. MAAE leading to treatment/study discontinuation) and AESIs which will be captured and tabulated in the outputs covering the whole study period (i.e. up to 12 months postpartum), and MAAEs which will be captured and tabulated for all participants from the first vaccination until 6 months after (each) vaccination.

Number and percentage of participants with at least one particular AE (unsolicited/solicited) will be tabulated. Unsolicited AEs will be summarized by System Organ Class and Preferred Term. Solicited AEs will be summarized by class (administration site/systemic) and Preferred Term.

For solicited AEs following tables will be provided: summary, by worst severity grade, at least grade 3, related (systemic only), time to onset (in days) and duration (in days) for most frequent events (>5%) and body temperature. Note: Duration is defined as number of days from the start of the event until resolution of the event. The time to first onset is defined as (date of first onset – reference date + 1). The reference date is the start date of the vaccination period.

For unsolicited AEs, the following tables will be provided: summary table (including SAE, AESI, MAAEs, AEs leading to treatment/study discontinuation, fatal outcome, and discontinuation), all events, most frequent (>5%), at least grade 3, related, and SAEs. The proportion of AEs resulting in a medically attended visit (other than routine health maintenance visits) will also be tabulated.

Pregnancy-related AEs in adult participants (including gestational diabetes, gestational hypertension, premature rupture of membranes, premature labor, premature uterine contractions, poor or restricted fetal growth, pre-eclampsia, eclampsia, vaginal or intrauterine hemorrhage [non-exhaustive]) will be tabulated separately. The complete list of preferred terms to be included as pregnancy related AEs is provided in Section 6.8.

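### The MAAE window in Section 5.3.1 runs to 6 months after the last vaccination, although the endpoint is defined for the first vaccination, so boosted Group 4 women get a longer primary window that takes in post-booster events

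*SAP*

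**What the plan says.** Section 5.3.1 (primary endpoints) heads its safety list "Safety and reactogenicity of Ad26.COV2.S (first vaccination) in adult participants". The solicited and unsolicited bullets are tied to that dose, for example "Unsolicited AEs for 28 days after (first) vaccination". The SAE/AESI bullet starts at the first vaccination and runs to the end of the study. The MAAE bullet reads "MAAEs until 6 months after the last vaccination". Section 5.4.1 gives the booster endpoint an MAAE bullet in the same words.

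Elsewhere the window is set per dose, or can be read that way. Section 1.1 gives, for the primary one-dose objective, "Medically-attended adverse events (MAAEs) until 6 months after vaccination", and repeats that limit under the booster objective. Section 5.6.1.3 speaks of "MAAEs which will be captured and tabulated for all participants from the first vaccination until 6 months after (each) vaccination". Section 5.3.3 sends the primary analysis there: the safety objectives "will be evaluated with AEs, SAEs, AESIs and MAAEs as detailed in Section 5.6.1".

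On who can have two doses, Section 1.2 says of Groups 1-3: "No further vaccinations will be received by these groups during the study". Group 4 (vaccine naïve at entry) may take an optional booster once pregnancy is over, at the earliest 2 months after the first study dose. The SAP states no upper limit on that interval.

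**The concern.** For a woman who receives one study dose, first and last vaccination are the same and nothing changes. For a boosted Group 4 woman, following 5.3.1 literally has two effects:

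- MAAEs that follow the second dose count towards the endpoint meant to describe the first.
- Her observation time is longer than that of every other participant.

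Section 5.1 uses the number of participants as denominator, not person-time. Section 5.6.1.5 counts those who report no event as event-free. Unequal follow-up therefore passes straight into the percentages. The study is purely descriptive, so these percentages, by vaccination-history group and overall, are the result that readers will use. Sharing one closing rule between 5.3.1 and 5.4.1 also blurs what distinguishes the primary MAAE endpoint from the booster one.

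**Working it through.** The plan gives no figure for MAAE risk or booster timing, so there is no stated number to reproduce. The check is window arithmetic, followed by an illustration.

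**1. Windows.** Let the booster be given d months after the first study dose, with d ≥ 2 (Section 1.2). In months from the first dose, before any cut for study end, withdrawal or an outside COVID-19 vaccine:

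- 6 months after the first dose: [0, 6]
- 6 months after the last dose (5.3.1, 5.4.1): [0, d + 6]
- 6 months after each dose (5.6.1.3): [0, 6] together with [d, d + 6]

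| Booster at month d | After first | After last | After each | Post-booster months inside a plain [0, 6] |
|---|---|---|---|---|
| none | 6 | 6 | 6 | 0 |
| 2 | 6 | 8 | 8 | 4 |
| 4 | 6 | 10 | 10 | 2 |
| 6 | 6 | 12 | 12 | 0 |
| 8 | 6 | 14 | 12 | 0 |
| 12 | 6 | 18 | 12 | 0 |

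The last-dose and each-dose rules cover the same time up to d = 6. Beyond that, the last-dose rule also counts the gap between month 6 and the booster (2 months at d = 8). The right-hand column shows that anchoring to the first dose does not by itself exclude booster time when d < 6; the window must also stop at the booster.

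**2. Do Tables 3 and 4 settle the cut?** Table 3 closes the post-dose 1, prepartum and postpartum phases one minute before the booster, so phase tables keep booster events apart. Its only limit at 6 months after the first dose is in Prepartum follow-up 1, which also ends at birth. Enrolment starts at Week 16. Assuming delivery near Week 40, birth comes at most 40 − 16 = 24 weeks after the dose, so that limit will rarely bind. No postpartum phase and no Table 4 interval ends 6 months after the first dose, and the entire-study interval spans both doses. The MAAE cut must therefore come from the endpoint text.

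**3. Where does it bite?** The primary analysis includes data up to the Day 42 postpartum visit (Section 5.8.2). On the same assumption, the longest follow-up at that visit is about 24 + 6 = 30 weeks. At most about 6 weeks of it can be post-booster, because the booster requires completed pregnancy. A woman dosed late in pregnancy has not reached 6 months by then. Her MAAE window is complete only at the final analysis, when booster data are present.

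**4. Illustration (assumed constant hazard; assumed 6-month risk r).** Risk over d + 6 months = 1 − (1 − r)^((d+6)/6).

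| r | d = 2 | d = 4 | d = 6 |
|---|---|---|---|
| 10% | 13.1% | 16.1% | 19.0% |
| 20% | 25.7% | 31.1% | 36.0% |
| 30% | 37.8% | 44.8% | 51.0% |

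For example, r = 20% and d = 2 gives 1 − 0.8^(8/6) = 25.7%. These are risks for a boosted woman. If a share s of Group 4 is boosted, the group figure is (1 − s) × r + s × (boosted risk). With r = 20%, d = 4 and assumed s of 25%, 50% or 75%, that is about 23%, 26% or 28%.

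**The case against.** The strongest reply is that the plan already separates the doses. Table 3 ends every pre-booster phase at the booster, and Table 4 defines a primary and a booster vaccination period for the vaccine-naïve group. The primary analysis holds little booster time, and no hypothesis is tested. For SAEs, AESIs and discontinuations, 5.3.1 deliberately runs through the whole study, so some post-booster events belong to the primary endpoint by design. This limits the reach of the problem but does not remove it. MAAEs are the one time-limited item in that list whose limit is tied to the wrong dose, and the phases do not supply the missing cut.

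Three stronger readings are tempting and not supported:

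- **Three mutually incompatible windows.** Section 1.1 states its limit once per objective and 5.6.1.3 states it per dose, so the two can be read as one rule. The firm conflict is per-dose against last-dose, and the each-dose and last-dose rules differ in covered time only for boosters after month 6.
- **Inflation across Group 4.** Only boosted women are affected, and the booster is optional.
- **A near-doubling of the primary analysis figures.** Windows of 12 months or more cannot arise by Day 42 postpartum under the delivery assumption above.

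It is also fair to object that ending the first-dose window at the booster creates a new imbalance: follow-up of min(6, d) months, so 2 months for a woman boosted at month 2. That stands and is taken up in the fix.

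**Conclusion.** The point holds in limited form. The MAAE bullet of 5.3.1 contradicts its own heading and neighbouring bullets, duplicates the booster endpoint in 5.4.1, and conflicts with the per-dose window in 1.1 and 5.6.1.3. Taken literally, it gives boosted Group 4 women a primary window of d + 6 months, at least 8, against 6 for all others. It thereby mixes post-booster events into endpoint-level and entire-study MAAE percentages, mainly at the final analysis.

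For a boosted woman, an assumed 20% six-month risk becomes 25.7% to 36.0% for boosters at months 2 to 6. The group-level shift is smaller and depends on booster uptake, which the SAP does not give. The window lengths follow from the text. The percentages rest on an assumed constant hazard and assumed base risks, and serve only to show scale.

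**What to change.** - **Section 5.3.1:** end the MAAE window 6 months after the first vaccination, and assign MAAEs with onset after the booster to the booster period. This matches Table 3, which already closes the pre-booster phases at the booster.
- **Section 5.4.1:** for the booster endpoint, count MAAEs from the booster until 6 months after it.
- **Section 5.6.1.3:** align the wording and tabulate the two windows separately. Add the first-dose MAAE interval to Table 4, since no existing interval ends at that point.
- **Reporting:** women boosted before month 6 will have a shorter first-dose window. Beside the Group 4 and overall MAAE percentages, give the number boosted before month 6 and the follow-up time, or an exposure-adjusted rate.

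The cost is wording in three sections, one derivation rule and a line or two in the MAAE tables. The dates needed are already used in the phase derivation, so no new data are required.
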